### **1.2.1 Previous and Ongoing Clinical Studies**

To date, balovaptan has been investigated in 5 completed Phase I studies including a proof-of-mechanism study in healthy volunteers (BP29412) in a total of 195 subjects. A Phase I relative bioavailability study (Study WP40038) comparing the Phase III tablet formulation with formulations used in previous Phase I and II studies is ongoing (clinically complete, reporting ongoing).

A Phase II study in 148 adult male ASD patients has been completed (BP28420, also referred to as VANILLA) and a Phase II study in 127 pediatric ASD patients (male and female) is ongoing (BP30153, also referred to as AV1ATION).

#### **1.2.1.1 Clinical Pharmacology**

Exposure of balovaptan increased in a greater than dose-proportional manner following single doses of 0.5 to 76 mg, whereas an approximately linear increase in exposure was observed after repeated dosing with 12 to 52 mg once daily (qd) for 14 days. Balovaptan was rapidly absorbed with a median time to maximum observed plasma concentration ( $T_{max}$ ) between 1 and 4.5 hours after administration of single doses and between 3 and 4 hours following multiple dosing. Steady state was achieved after approximately 7 days; the mean apparent elimination half-life ( $T_{1/2}$ ) after the last dose (Day 14) was approximately 46 hours. Food had no relevant effect on the PK of balovaptan.

In the human mass balance study (Study BP29279), an almost complete absorption of the study drug was observed within the first 72 hours following administration.

The majority of excretion of drug-related material occurred within the first 7 days. Renal excretion was found to be the major pathway of elimination (approximately 53% of the material recovered, mostly composed of metabolites) with the primary route of excretion via metabolism to M1 ( [REDACTED] ) into urine, accounting for approximately 23% of the dose. A further 30% of the administered dose was recovered in feces.

In plasma, steady state exposure to the [REDACTED] metabolite M3 was similar to or slightly higher than that of balovaptan and exposure to the [REDACTED] metabolite M2 was lower than that of parent. M3 and M2 qualify as major metabolites in plasma.

[REDACTED]

There was no clinically/statistically relevant PK interaction with the P-glycoprotein substrate risperidone, one of only 2 approved medications for ASD symptoms in the US, and fluoxetine, a weak CYP3A4 inhibitor often used to treat associated symptoms of ASD. Administration of a single dose of balovaptan 12 mg in combination with itraconazole, a strong CYP3A4 inhibitor, resulted in an increase in the exposure of balovaptan by 1.4-fold for  $C_{max}$  and an approximately 3.1-fold increase for area under the concentration vs time curve from time 0 to 120 hours ( $AUC_{0-120h}$ ). The exposure of metabolite M3 was 1.92- and 1.82-fold lower in terms of  $C_{max}$  and  $AUC_{0-120h}$ , respectively.

#### **1.2.1.2 Safety**

To date, balovaptan has been found to be safe and well tolerated in clinical trials. No particular safety concern has emerged and no adverse drug reactions have been identified. More specifically, creatine phosphokinase (CPK) was monitored in previous trials based on observations of muscle toxicity in rats; no changes of any importance were noticed. Similarly, no hematology or neurotoxicity findings have been observed in clinical trials. The maximum tolerated dose was not reached in either the single ascending dose (SAD) study with single doses (up to 76 mg) or the multiple ascending dose (MAD) study with multiple doses (up to 52 mg qd for 14 days) in healthy subjects. In light of convulsions observed in dogs, dose escalation was stopped so as not to exceed a  $C_{max}$  (mean) of 810 ng/mL in the SAD and MAD studies. In healthy volunteer studies, one serious adverse event (SAE) of bacterial infection (suspected Lyme disease) was reported in Study BP29412; this SAE was considered unrelated to study drug.

Balovaptan has also been found to be safe and well tolerated in male patients with ASD at doses up to 10 mg/day (highest dose administered) for a period of 12 weeks (Study BP28420). No particular safety patterns attributable to the administration of balovaptan were identified. A total of 8 SAEs (all but one [rhabdomyolysis] considered unrelated to study drug) in 4 patients and 1 adverse event of special interest

(neutropenia) were reported in the study. No relevant safety concern has emerged from the recently started study in ASD pediatric patients (BP30153).

Based on the review of all available data, it is currently recommended not to exceed a plasma exposure equivalent to 20 mg qd in adult subjects in clinical trials with a continuous treatment duration longer than 4 weeks.

Refer to the Investigator's Brochure for details on nonclinical and clinical studies.

### **1.3 STUDY RATIONALE AND BENEFIT-RISK ASSESSMENT**

The study will be performed in healthy subjects who will not receive any health benefit from participating in this study. The study is necessary for the further development of balovaptan and may be of benefit for future patients.

To date, balovaptan has been investigated in 195 healthy subjects in 5 completed Phase 1 studies (Studies BP25694, BP28318, BP28977, BP29279, and BP29412). One oral relative bioavailability study (Study WP40038) is ongoing (clinically complete, reporting ongoing).

Additionally, balovaptan was investigated in a Phase II study in 148 adult male patients with ASD (BP28420, "VANILLA").

Adverse event (AE) reporting in healthy subjects did not reveal any particular safety alert for balovaptan. The most frequently reported AE was headache, without an apparent dose-response relationship for balovaptan. For the vast majority of AEs, the intensity was rated as mild or moderate. The dose range in these studies was 0.5 to 76 mg (single dose) and 12 to 52 mg (multiple doses for 14 days).

The effect of inhibition of CYP3A4 was previously investigated using a single dose of 12 mg of balovaptan. The study showed that balovaptan  $AUC_{0-120h}$  increased by 3.1-fold and  $C_{max}$  by 1.4-fold in the presence of itraconazole. Mean  $AUC_{0-120h}$  and  $C_{max}$  metabolite M3 were 1.82- and 1.92-fold lower, respectively, in the presence of itraconazole than in the absence of itraconazole. M2 was not measured in that study.

The current study is designed to assess the effect of inhibition of CYP3A4 on the steady state pharmacokinetics of balovaptan after 15 days of coadministration with itraconazole, as balovaptan showed dose and time-dependent PK. Although not reliably measured, analysis of  $AUC_{0-inf}$  in the presence of itraconazole indicated a 4.6-fold increase in balovaptan exposure and plasma  $T_{1/2}$  indicated an increase from 27 to 80 hours. The mean (SD)  $C_{max}$  and  $AUC_{0-T}$  for parent following 14 days of dosing with balovaptan 52 mg qd was 484 (43.1) ng/mL and 5920 (817) h·ng/mL, respectively. M3 was only measured after balovaptan 40 mg for 14 days: the mean (SD)  $C_{max}$  and  $AUC_{0-T}$  were 264 (45.4) ng/mL and 5260 (807) and h·ng/mL, respectively.

Due to the anticipated increase in balovaptan exposure when administered with itraconazole, to ensure optimal subject safety, the study design includes a sentinel group of 4 subjects, who will be dosed with 5 mg balovaptan qd. The dose may be increased to the targeted clinical dose, 10 mg, only if exposure data from the sentinel cohort are acceptable (see Section 3.1 for exposure criteria), and no safety concerns have emerged in the opinion of the Investigator or Sponsor's Medical Monitor.

Itraconazole is generally well tolerated. Gastrointestinal disturbances are the most frequently reported AEs following the oral use of itraconazole. Nausea and vomiting have been reported in about 11% and 5% of patients undergoing treatment of systemic fungal infections, respectively, diarrhea in 3%, and abdominal pain in about 2%. These AEs are dose-related and may be minimized by giving itraconazole with food. Rash was observed in 9% of patients, however rash tends to occur more frequently in immunocompromised patients receiving immunosuppressive medications. Itraconazole has been associated with rare cases of serious hepatotoxicity. Some of these cases had neither pre-existing liver disease nor a serious underlying medical condition, and some of these cases developed within the first week of treatment. Other adverse effects include pruritus and angioedema, and rare cases of anaphylaxis have been reported. Fatigue, headache, dizziness, hypertension, decreased libido, impotence, and somnolence may also occur (Janssen Pharmaceuticals, 2001).

## **2. OBJECTIVES AND ENDPOINTS**

This study will investigate the effect of itraconazole treatment on the PK of balovaptan and its major metabolites M2 and M3. [Table 1](#) presents the objectives and endpoints.

**Table 1 Objectives and Corresponding Endpoints**

Objectives	Endpoints
Primary	
To investigate the effect of itraconazole treatment on the PK of balovaptan and its major metabolites M2 (as applicable) and M3, at steady state	
Primary PK endpoints: balovaptan, M2, and M3 <math>C_{max}</math> and area under the concentration vs time curve over the dosing interval (<math>AUC_{0-T}</math>) after 15 days of balovaptan qd dosing in Period 2, and after 10 days of balovaptan qd dosing in Period 1
 
Additional PK endpoints: balovaptan, M2, and M3 time to maximum observed plasma concentration (<math>T_{max}</math>), trough plasma concentration (<math>C_{trough}</math>), and time to steady state

Secondary	
To explore the safety and tolerability of balovaptan when given alone and in combination with itraconazole in healthy subjects.	Adverse events (AEs), clinical laboratory values, vital signs, electrocardiogram (ECG), and physical examination
Tertiary/Exploratory	
Relationship between the CYP3A4 genotype, among others, a and steady state balovaptan exposure, and the influence of the CYP3A4 genotype, among others, on the effect of itraconazole on balovaptan PK	The pharmacogenetics b of metabolizing enzyme, transferases, transporters, etc, possibly involved in the absorption, distribution, metabolism, and excretion of balovaptan and its major metabolites (eg, CYP3A4 and P-glycoprotein)
The plasma exposure of itraconazole and hydroxy-itraconazole	Area under the curve from time 0 to 24 hours ( $AUC_{0-24h}$ ), $C_{max}$ , and $T_{max}$ on Day 5 and Day 20

aThe relationship between other genotypes and PK of balovaptan may also be exploredbResults may be pooled with data from other studies of balovaptan.

### **3. STUDY DESIGN**

#### **3.1 DESCRIPTION OF THE STUDY**

This study will be non-randomized, open-label, one-sequence, two-period within-subject study to investigate the effect of CYP3A inhibition on the PK of balovaptan in healthy male and female volunteers using itraconazole as a CYP3A inhibitor. The study will be conducted at 1 site in the Netherlands.

Subjects will be screened for eligibility for the study for up to 28 days before the first dose of study drug. In Period 1, eligible subjects will be admitted to the clinical research unit (CRU) in the afternoon of Day -1 and remain in the CRU until discharge in the morning of Day 11. There will be at least a 7-day washout between the last dose in Period 1 and the first dose in Period 2. After this washout period, subjects will return to the CRU on Day -1 of Period 2 and remain in the CRU until discharge on Day 21 of Period 2. For each study period, dosing will begin on Day 1.

Subjects will receive the following study drugs in 2 periods over a total of 37 days:

##### Period 1:

[figure not shown]
- Days 1 to 10: oral balovaptan once daily (qd)
- Days 11 to 17: no study drug

##### Period 2:

- Days 1 to 5: 200 mg itraconazole twice daily, approximately 12 hours apart (on Day 5, only the AM dose of itraconazole will be administered)
- Days 6 to 20: balovaptan qd + 200 mg itraconazole qd

Figure 1 presents an overview of the study design. A schedule of activities is provided in Appendix 1.

**Figure 1 Study Schema**

Abbreviations: bid = twice daily; PK = pharmacokinetics; qd = once daily

On Period 1 Day 10 and Period 2 Day 20, balovaptan will be dosed at the same time of day. On Period 2 Days 5 and 20 itraconazole will be dosed at the same time of day. On Period 2 Days 6 to 20, itraconazole will be administered in combination with balovaptan.

Subjects will undergo study assessments and procedures, including assessments of AEs and concomitant medications, vital signs, 12-lead ECGs, clinical laboratory evaluations and blood sampling for PK assessments and genotyping as per the schedule of assessments in Appendix 1.

The dose of balovaptan to be used during balovaptan alone and balovaptan plus itraconazole dosing periods will be 5 mg qd for an initial sentinel cohort of 4 subjects (Cohort A). The safety, tolerability, and PK data up to 24 hours after the final dose of balovaptan (when given in conjunction with itraconazole), for at least 3 of the 4 subjects,

will be reviewed by the by the Sponsor's Medical Monitor or designee and the Investigator. There will be at least a 20-day period between Cohort A and Cohort B to allow for analysis of PK data. After review of the data, a dose of balovaptan will be selected for the remainder of subjects (Cohort B). The dose may remain 5 mg qd or may be increased to 10 mg qd, depending on data from Cohort A. The dose may be increased to 10 mg qd for Cohort B if the highest mean exposure values for  $C_{max}$  and  $AUC_{[0-1]}$  in the presence of itraconazole in Cohort A and the projected exposures expected for Cohort B do not exceed the highest exposures seen with multiple dosing of balovaptan 52 mg ( $484 \pm 43.1$  ng/mL for  $C_{max}$  and  $5920 \pm 817$  h-ng/mL for  $AUC_{tau}$ ) and there are no prohibitive safety findings based on a review of safety data from Cohort A. If these criteria are not met, dosing will be continued at 5 mg qd in Cohort B.

If a decision is made to keep the dose at 5 mg qd, a total of 10 subjects will enter Cohort B. If a decision is made to increase the dose to 10 mg qd, a total of 14 subjects will enter Cohort B.

### **3.2 END OF STUDY AND LENGTH OF STUDY**

The end of this study is defined as the date when the last subject, last visit (LSLV) occurs or safety follow-up is received from the last subject, whichever occurs later. The end of the study is expected to occur 12 weeks after the last subject is enrolled.

The total length of the study, from screening of the first subject to the end of the study, is expected to be approximately 15 weeks.

### **3.3 RATIONALE FOR STUDY DESIGN**

#### **3.3.1 Rationale for Open Label Design**

The primary objective in this study is to assess to what extent exposure to balovaptan after repeat dosing may change in the presence of the CYP3A4 inhibitor itraconazole. As such, drug concentrations in plasma are assumed to be objective measurements, which cannot be affected by volunteer or staff behavior. This is different for tolerability reporting, for which it is conceivable that knowing what treatment is being administered may affect reporting or causality interpretation. Therefore, it is generally accepted to conduct drug-drug interaction (DDI) studies with PK or pharmacodynamic (PD) primary endpoints using an open-label design, without placebo treatments, and since evaluation of safety and tolerability is only a secondary objective, an open-label design was deemed appropriate.

#### **3.3.2 Rationale for Balovaptan and Itraconazole Dose and Schedule**

##### **3.3.2.1 Balovaptan**

A dose of 10 mg balovaptan has shown statistically significant changes in efficacy parameters in adult patients with ASD and is the current proposed dose for Phase 3 trials in adults. However, it is to be expected that exposure in the presence of itraconazole may increase, based on the effect of itraconazole on the exposure of a

single dose of 12 mg balovaptan (at least 3.1-fold increase in  $AUC_{0-120h}$  and 1.4-fold increase in  $C_{max}$ ).

Therefore, in the current study, the effect of itraconazole on the multiple dose PK of a low dose of 5 mg balovaptan qd will initially be assessed in a sentinel group of 4 subjects, in order to assess whether it will be safe to assess the effect of itraconazole on the higher, clinically relevant dose of 10 mg. Single doses of balovaptan up to 76 mg and multiple doses up to 52 mg qd for 14 days were well tolerated. The mean exposure seen with multiple dosing of balovaptan 52 mg was  $484 \pm 43.1$  ng/mL for  $C_{max}$  and  $5920 \pm 817$  h·ng/mL for  $AUC_{0-T}$ .

Balovaptan is being developed for use in ASD, so it is expected that patients will need to take it for prolonged periods of time, likely for years or for life. Hence multiple dose testing is relevant from a clinical point of view. The multiple dose PK of balovaptan with 14 days of dosing was previously characterized in humans and was found to be time and dose dependent. Accumulation was observed with multiple dosing, and steady state of parent and M3 was observed after approximately 7 days of dosing; the time to steady state has only been evaluated with sparse PK measurements for M2. Population modelling indicates that steady state of parent, M2, and M3 following a dose of balovaptan 10 mg is reached later (after around 10 days). In the presence of itraconazole, an increase in plasma  $T_{1/2}$  from 27 to 80 hours was observed. Based on these observations, the maximum level of DDI due to inhibition of CYP3A4 is expected to be observed with 15 days of coadministration of itraconazole with balovaptan, based on a predicted  $T_{1/2}$  of ~ 80 hours for balovaptan when combined with itraconazole.

In addition, exposure to the metabolite M2 has not been previously characterized with intensive PK sampling after multiple doses in humans, and this will also be achieved in the current design.

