16.2.2.1 Drug-Drug Interaction

The effect of itraconazole on the PK of balovaptan on Analysis Days 10 and 15 will be assessed. A linear mixed effect model will be used to analyze the natural log-transformed C_{max} and AUC_{0-tau} values of balovaptan, M2 and M3. An analysis variable representing the combination of treatment and analysis day (balovaptan alone on Day 10, balovaptan + itraconazole on Day 10, and balovaptan + itraconazole on Day 15) will be used as fixed effect and subject will be used as a random effect. The estimates for the differences between

- 1) balovaptan + itraconazole on Day 15 (test) and balovaptan alone on Day 10 (reference)
- 2) balovaptan + itraconazole on Day 10 (test) and balovaptan alone on Day 10 (reference)

will be back-transformed to derive the geometric mean ratios of balovaptan + itraconazole (on Days 10 and 15) over balovaptan alone on Day 10 together with the corresponding 90% CIs for the comparisons of the PK parameters.

In addition, as an exploratory analysis, the CYP3A4 genotype will be added as a factor. The relationship between other genotypes may also be explored.

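### The 15-day combination period is justified by a single-dose half-life that is not reconciled with the repeat-dose one, and the SAP has no analysis to show whether Day 20 is at steady state

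*Protocol*

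**What the plan says.** **Length of the combination period.** Protocol Section 3.3.2.1 states that "the maximum level of DDI due to inhibition of CYP3A4 is expected to be observed with 15 days of coadministration of itraconazole with balovaptan" and rests this on a predicted half-life of about 80 h with itraconazole.

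**Source of the 80 h.** Section 1.3 says: "The effect of inhibition of CYP3A4 was previously investigated using a single dose of 12 mg of balovaptan". A later sentence in that section opens "Although not reliably measured, analysis of" the AUC extrapolated to infinity (a 4.6-fold increase), and adds that the plasma half-life "indicated an increase from 27 to 80 hours". The caveat is attached to the extrapolated AUC, but the half-life stands in the same sentence. Section 1.3 also explains why a repeat-dose study is needed: "as balovaptan showed dose and time-dependent PK".

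**Repeat dosing without itraconazole.** Section 1.2.1.1 reports that the half-life "after the last dose (Day 14) was approximately 46 hours". It also says: "Steady state was achieved after approximately 7 days". Section 3.3.2.1 adds a modelled time to steady state of around 10 days at 10 mg. It does not mention the 46 h.

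**Endpoints.** Protocol Table 1 and SAP Section 5.1.2 list trough concentration and time to steady state for balovaptan, M2 and M3.

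**Analysis.** SAP Table 3 defines only Cmax, Tmax and AUC. SAP Section 16.2.2.1 compares the combination on Analysis Day 15, and again on Analysis Day 10, with balovaptan alone. It does not compare the two combination days with each other. Trough concentrations are tabulated and plotted by day, without an estimate or a criterion. SAP Section 7.1 states that there are no changes from the protocol.

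**The concern.** The trial repeats doses of a drug whose kinetics the protocol calls dose and time dependent, but the length of its test period is set by a half-life seen after one dose. The repeat-dose half-life alone is 46 h rather than 27 h. If the half-life under itraconazole is also longer on repeat dosing, the combination is still accumulating on Day 20 while the reference on Period 1 Day 10 is almost complete. The shortfall then falls mainly on the numerator of the ratio.

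For the parent drug, this makes the interaction look smaller than it is at steady state, for a product that the protocol expects to be taken for years. M3 fell with itraconazole in the single-dose study, so for M3 a ratio that is too low would overstate the decrease. The documents give no half-life for M3 under itraconazole, so that effect cannot be sized.

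As the SAP stands, the Day 15 ratio would be reported against a steady-state objective whether or not steady state had been reached.

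**Working it through.** **Inputs.** 15 daily combination doses before the end of the primary profile, and 10 in Period 1 (Section 3.1). Half-lives of 27 h and 80 h (Section 1.3) and 46 h (Section 1.2.1.1). Within-subject CV of 39% and n = 12 (Section 6.1).

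**Formula.** With linear one-compartment accumulation, the fraction of steady-state AUC over the dosing interval after N daily doses is F = 1 − 2^(−24N/T½).

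**The plan's own premise.** At 80 h, 15 days is 360/80 = 4.5 half-lives, so F = 1 − 2^(−4.5) = 95.6%. The time to 95% is 80 × ln(20)/ln(2)/24 = 14.4 days. The 15 days therefore follow from 80 h, with little to spare.

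**Reference.** At 46 h, 10 doses give F = 1 − 2^(−240/46) = 97.3%.

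**If the single-dose fold change applied to 46 h** (assumption): 46 × 80/27 = 136 h, and 15 days is 2.6 half-lives.

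| Half-life with itraconazole | F after 15 doses | Observed ratio ÷ steady-state ratio | Expected AUC, Day 15 ÷ Day 10 |
|---|---|---|---|
| 80 h | 95.6% | 0.956/0.973 = 0.98 | 1.09 |
| 100 h | 91.8% | 0.94 | 1.13 |
| 120 h | 87.5% | 0.90 | 1.17 |
| 136 h | 84.0% | 0.840/0.973 = 0.86 | 1.19 |

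For illustration, a true steady-state ratio of 4.6 would read about 4.52 at 80 h and 3.97 at 136 h. If the reference accumulated as at 27 h (F = 99.8%), the shortfall at 80 h would be 4% rather than 2% (0.956/0.998 = 0.96).

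**The protocol's times to steady state, scaled to 80 h.** The modelled 10 days is 240/46 = 5.2 half-lives, which at 80 h takes 17.4 days. The observed 7 days is 168/46 = 3.65 half-lives, which at 80 h takes 12.2 days. The two figures fall on either side of 15 days.

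**Precision of a Day 15 versus Day 10 contrast.** The log-scale SD is √ln(1 + 0.39²) = 0.376. With 12 subjects and three conditions there are 22 degrees of freedom, and the 90% CI factor is exp(1.717 × 0.376 × √(2/12)) = 1.30. An estimate of 1.09 has an interval of 0.84 to 1.42, which includes 1.19. The contrast alone cannot separate the two cases at this CV.

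**Precision of a trough fit.** I simulated a one-exponential fit to the combination troughs on Analysis Days 3 to 16, with 12 subjects and half-life varying between subjects by 0 or 25%. The residual CVs of 10% and 20% are assumptions; 39% is the documented within-subject value for AUC. The 5th to 95th percentiles of estimated F on Analysis Day 15, over both settings, were:

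| Residual CV | Truth 95.6% (80 h) | Truth 84.0% (136 h) |
|---|---|---|
| 10% to 20% | 0.93 to 0.98 | 0.77 to 0.90 |
| 39% | 0.90 to 0.99 | 0.71 to 0.92 |

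The cases separate at 10% to 20% and overlap slightly at 39%.

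**The case against.** A reader might infer that Day 20 falls well short of steady state and that the ratio is about 14% too low. The documents do not support this, for four reasons.

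- **The 136 h is an extrapolation.** On the protocol's own 80 h the ratio is only about 2% low. Balovaptan is mainly metabolised by CYP3A4. If the rise from 27 h to 46 h is itself a loss of CYP3A4 clearance, it overlaps with what itraconazole removes. In rate terms, ln(2)/27 − ln(2)/46 = 0.0106 per hour is lost on repeat dosing, against ln(2)/27 − ln(2)/80 = 0.0170 per hour with itraconazole. The half-life under inhibition could then stay near 80 h. The documents do not say which mechanism applies.
- **The 46 h may not govern accumulation.** It comes from 12 to 52 mg, not 5 or 10 mg. At 52 mg, Cmax over average concentration is 484/(5920/24) = 1.96, whereas one compartment at 46 h allows at most 1.19. The formula fits the repeat-dose profile poorly and may overstate the shortfall.
- **The protocol may have a further basis.** It calls 80 h predicted, it uses population modelling nearby, and parts of the background are redacted.
- **Relevant data are already collected.** Troughs are plotted by day. Dividing the two SAP ratios gives the Day 15 versus Day 10 estimate, though without a confidence interval.

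All four limit the size of the problem. None supplies the missing reconciliation of 46 h with 80 h, or a method for the two endpoints that the protocol names.

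It is also tempting to call the error conservative or unsafe in general. The understatement applies to the parent; for M3 the same shortfall would exaggerate the effect.

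**Conclusion.** The point holds in a limited form. The duration rationale leaves a single-dose 80 h and a repeat-dose 46 h unreconciled. Day 20 could lie between about 84% and 96% of steady state, and the parent AUC ratio could be about 2% to 14% low. The lower figure rests on the protocol's 80 h. The upper one rests on proportional scaling, which is not in the documents. Both assume one-compartment accumulation and a 46 h reference.

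The firmer finding is in the SAP. Trough concentration and time to steady state are stated endpoints, but no parameter, estimate or output is planned for either beyond concentration tables and plots, despite the statement that nothing changed from the protocol. The steady-state premise of the primary result would go untested although the scheduled samples can inform it. This is worth correcting before database lock. It does not show that the design fails.

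**What to change.** All changes use data already scheduled. No change to dosing, visits or samples is proposed.

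1. **SAP Section 16.1.2 and Table 3.** Add trough concentration and a time-to-steady-state analysis, with matching outputs in SAP Appendix 4. For balovaptan, fit an exponential approach to plateau to the combination troughs (Analysis Days 3 to 16) and report the estimated fraction of steady state on Analysis Day 15 with its 90% CI. For M2 and M3 report the trough trend only, since a one-exponential form is not justified for metabolites.
2. **SAP Section 16.2.2.1.** Add the combination Day 15 versus Day 10 contrast for Cmax and AUC over the dosing interval, with 90% CI from the existing model. Label it supportive, because its CI factor is about 1.30.
3. **Reporting.** If these analyses indicate continued accumulation, describe the primary ratio as the effect after 15 days of coadministration rather than as the steady-state effect. Avoid a hard 95% cut-off: with a true half-life of exactly 80 h, the simulated fit fell below 95% in about one trial in five at 10% residual CV and about two in five at 39%.
4. **Protocol Section 3.3.2.1.** Reconcile the 46 h and 80 h figures and state why 80 h is expected on repeat dosing. Do not enter 136 h as fact.

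The cost is SAP wording, one fit and one contrast. The downside is that the trough fit depends on its model and can be imprecise, so it should support the primary ratio and not replace it.
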